3 RISKS AND BENEFITS OF THE INVESTIGATIONAL DEVICE AND CLINICAL INVESTIGATION

3.1 Anticipated clinical benefits

It is anticipated and hypothesised that a clinically effective Liver Dialysis Device (LDD) could reduce deaths from liver failure, allow earlier discharge from intensive care and in a proportion of patients, prolong survival without transplantation.

Patient groups that could benefit from the device include:

- Patients with ALF and ACLF: preventing need for transplantation or serve as a bridge to transplantation in ALF, and aiding recovery to pre-event level of liver function in ACLF;
- Patients with decompensated cirrhosis who are waiting for a transplant: preventing clinical deterioration while
 on a waiting list thereby reducing mortality;
- Patients with decompensated cirrhosis not considered suitable for transplantation: long term dialysis to improve survival;
- Patients with intractable pruritus and/or fatigue: improve quality of life and prevent need for transplantation.

The following patients may also benefit:

 Multiple organ dysfunction in intensive care – almost all patients with critical illness have endotoxemia which contributes to inflammation;

- Alzheimer's disease and stroke albumin is dysfunctional in these conditions where plasmapheresis has been found to be beneficial;
- Intoxication from protein bound substances protein bound toxins such as drugs and biological weapons may be treatable with albumin exchange;
- Cholestatic syndromes: such as porphyria, in-born errors of metabolism, drug related cholestasis and graft versus host disease;
- Severe iron accumulation treatment of heart failure due to iron overload as albumin can bind iron.

Clinical Investigation Plan CIP YAQ-002 Version: 7.0 10 Octobe	er 2019
--	---------

3.2 Anticipated adverse device effects associated with DIALIVE

The procedural and device risks associated with the indicated use of the septeX™ and oXiris® filters in summary are:

Risk	Mitigation
Blood loss, e.g. leading to organ failure - exsanguination from extracorporeal blood circuit - exsanguination via haemofilter to dialysing fluid circuit - coagulopathy associated with extracorporeal therapies	- CVVHD/HF/HDF via CVC is long established - septeX™ sets are indicated for CVVHD, and cytokine removal - oXiris® sets are indicated for CVVHDF, and endotoxin adsorption and cytokine adsorption - UCL studies of LDD in a porcine PALF model (series septeX™ and oXiris® using Prismaflex platform) showed experimental arrangement to be compatible, biocompatible and safe - CIP specifies ICU/HDU monitoring particularly monitoring: -liver function -cardiovascular function -cerebral function -renal function -pulmonary function -albumin and immune function
Air embolism, eg leading to ischaemia, congestion, metabolic dysfunction, reperfusion injury et sequelae: — air introduced via extracorporeal blood circuit — air introduced via haemofilter membrane from dialysing fluid circuit — air introduced via anticoagulant infusion	Prismaflex control unit, indicated for CVVHD, HF and CVVHDF, controls and monitors extracorporeal circuit: o physiological flow rates o air ingress o blood loss

Thromboembolism, e.g. leading to congestion and organ failure: CVVHDF, controls and monitors extracorporeal circuit: particulates degradation products physiological flow rates air ingress 0 blood loss septeX™ and oXiris® sets MDD CE'd for CRRT applications septeX™, oXiris® sets and extension tube are: Haematological risks: haemolysis (mechanical and chemical lysis) assured compatibility with blood (ISO anaemia 10993-4) leucopenia CE marked (93/42/EEC) thrombocytopenia Complaints data do not identify issue altered function of cells hypoalbuminemia thrombosis platelet activation complement system activation (inflammation) septeX™ and oXiris® sets MDD CE'd for CRRT Material medicated toxaemia, including those arising from applications leachables, particulate, degradation products and incompatibility with packaging: cytotoxicity hypersensitisation irritation systemic toxicity genotoxicity carcinogenicity immunotoxicity reproductive/developmental toxicity pyrogenic fever septeX[™] . oXiris® sets and extension tube are: Contamination – production, transport and storage induced infection (transmissible agents may include bacteria (and terminally sterilized EtO (ISO11135-1) endo/exo toxins), mould, yeast, parasites and unclassified validated primary packaging pathogens: CE marked (93/42/EEC) fever unadulterated septicaemia single-use only lupus organ failure - interconnection and priming uses aseptic technique

·	.
Performance degradation - adsorption of plasma proteins, lipids, calcium - adhesion of platelets, leukocytes or erythrocytes - potential mechanical haemolysis	
Misuse of the LDD by clinical staff not qualified to deal with;	The DIALIVE is only available:
 adverse events exsanguination thromboembolism clotting exacerbation of symptoms and complications of liver failure death 	 to the named investigator exclusively for clinical investigation under approved CIP (SAFETY Clinical Investigation) potential future benefits outweigh CIP risks
resulting from delivery of liver dialysis support	potential value of an analygic on the state of the state
	Set-up and Priming
	 septeX[™] barcode removed so that treatment parameters can be set manually
	 septeX[™] set loaded as normal
	oXiris® dialyzer aseptically connected using extension tube
	 septeX™ and oXiris® set primed in series (auto prime followed by manual prime)
	oXiris® blood return line substituted on Prismaflex for septeXTM blood return line
	air removal of oXiris® dialyser finished by hand
	complete by clamping off oXiris® dialysing fluid-effluent circuit
	Operation
	Prismaflex control, monitoring and safety features all engaged
	 CVVHDF proceeds as indicated except blood path series connection of septeX[™] and oXiris®
	ICU/HD monitoring per CIP and institutional standard of care
	Restitution of all extracorporeal blood during

Clinical Investigation Plan

CIP YAQ-002

Version: 7.0 10 October 2019

	Clinical Investigation Plan	CIP YAQ-002		Version: 7.0 10 October 2019
				 
				d at end of session, except in case of filter thing.
Circumventing of Prismaflex monitoring and control features:		Function	onal compatibility of Prismaflex, septeX™	
-	LDD adverse events		set + o	(iris® set verified in porcine model
- exanguination - thromboembolism		Prisma	iflex pre-programmed sequential	

clotting exacerbation of symptoms and complications of liver failure

death

mistakes Prismaflex control, monitoring and safety features

procedures mostly eliminate slips, lapses and

Prismaflex CE marked for CVVHDF

engaged

Investigator familiarity with CVVHDF

Use is restricted to qualified investigator and supervised qualified support familiar with aseptic technique and liver failure patients

Blood loss due to venous cannulation

- Undertaken by experienced staff trained in the procedure
- Standard clinical procedures are followed
- Coagulation results reviewed prior to cannulation
- CIP specifies ICU/HDU monitoring particularly monitoring:
 - liver function
 - cardiovascular function
 - renal function

Hypotension induced by DIALIVE, especially in patients who may be intravascularly depleted because of fluid restriction, diuretic therapy, inadequate oral intake and anemia, or those with evidence of vasoplegia.

- perform fluid preloading
- simultaneous replacement of lost albumin
- stepwise increase of blood flow rate through the **DIALIVE**
- stepwise increase of replacement fluid
- closely monitor the patient

3.3 Residual risks associated with participation in the clinical investigation.

The risks associated with intermittent haemodialysis (HD) and continuous haemodiafiltration (HF) are well established and understood. Similarly the risks associated with intravenous albumin delivery for replacement of blood loss are well known. Both procedures constitute normal SOC. Risks associated with the use of an extracorporeal circulation, known as the "first use syndrome", is not specifically related to the DIALIVE but rather a risk associated with any type of extracorporeal circulation exposure. Well established protocols exist to adjust the condition by experienced medical staff.

3.4 Possible interactions with concomitant medical treatments

Heparin and/or Epoprostenol will be administered to keep the circuit open and the amount used will be dependent upon the clotting profile of the patient determined by their platelet count, prothrombin time, partial thromboplastin time and fibrinogen. Clotting may be corrected by the administration of clotting products as required prior to insertion of the central line and will be decided on a case by case basis.

There is a potential for elimination of albumin bound and water soluble drugs, but there are well established protocols for dose adjustments during haemofiltration particularly for drugs such as antibiotics.

Terlipressin: Should only be administered in patients diagnosed with hepatorenal syndrome according to the ICA guidelines. In case a patient has a variceal bleed, terlipressin can be administered as per protocol. The use of terlipressin for these indications are for splanchnic vasoconstriction and not as a pressor for systemic hypotension.

Lactulose and Rifaximin: Should only be commenced in patients if they have clinical evidence of hepatic encephalopathy. They may be continued on Lactulose and Rifaximin if they were receiving it at the time of randomization.

Albumin: The use of albumin should be restricted for evidence-based indications. These include: a diagnosis of spontaneous bacterial peritonitis, hepatorenal syndrome and large volume paracentesis (>2 litres). Risks associated with albumin administration are well known and appropriately taken care of by medical staff.

Beta-blockers: A). Should be continued in patients receiving it at the time of randomization unless the patients is hypotensive in which case the dose either be reduced or the drug stopped If this is stopped completely, alternative medications such as octreotide may be used per local policies. B) should not be started if the patient is not receiving it at the time of screening.

3.5 Steps that will be taken to control or mitigate the risks

All hazards associated with the intended use of DIALIVE including single fault conditions where applicable, have been identified and evaluated. The process of risk reduction has not introduced any new risks that have not been overlooked and further risk control measures are judged to be unnecessary.

On the basis of the risk management report, the technological solutions and organisational measures for qualifying and monitoring subjects implemented in the proposed protocol, including compliance with relevant safety, performance and clinical care standards, any residual risk are judged to be very low or as low as reasonably practicable and acceptable when weighed against the anticipated patient benefits as elicited from the clinical investigation.

Clinical Investigation Plan CIP YAQ-002 Version: 7.0 10 October 2019
--

Regular safety review and recommendations will be performed by individual expert investigators and by the members of the TMG and DSMB to mitigate any potential risks associated with DIALIVE therapy. New recommendations will be implemented at appropriate iterations of the protocol versions.

3.6 Risk-to-benefit rationale

The series connection of the septeX[™] and oXiris® dialyser sets extends the risks addressed in section 3.2 without the introduction of new risks in respect of:

- infection;
- blood loss;
- air ingress.

The risk analysis, risk-to-benefit assessment and risk control is described in detail in the Investigator's Brochure (IB). After risk mitigation, no hazards remain with an unacceptable risk level.

Clinical Investigation Plan CIP YAQ-002 Version: 7.0 10 0	October 2019
---	--------------

4 OBJECTIVES AND HYPOTHESES OF THE CLINICAL INVESTIGATION

4.1 Objectives, primary and secondary

Primary Objective

To evaluate the safety of the DIALIVE in patients with alcohol related cirrhosis with Acute on Chronic Liver Failure Grades 1, 2 and 3a (ACLF) compared with the group treated with standard of care.

Secondary Objective

To evaluate the performance of the DIALIVE in the above mentioned patient group. To evaluate clinical benefit in patients receiving DIALIVE treatment plus Standard of Care (SOC) versus SOC alone.

4.2 Hypotheses and claims

The underlying hypothesis is that DIALIVE will significantly improve the prognosis of patients with ACLF by i) exchanging irreversibly damaged native albumin, which accumulates during this disease process and is ineffective in its function, with fresh albumin, and ii) removal of endotoxins, inflammation and endotoxaemia being the central pathogenetic feature of this illness.

This is a first into man study of a novel Liver Dialysis Device. No specific hypothesis is to be statistically assessed in this first feasibility study. Randomization of patients is implemented to obtain unbiased clinical data appropriately balanced between SoC and DIALIVE treated patients to provide fundamental learning data on the outcome of treatment in both study arms, in line with the recommendations of the DSMB (see appendix 7). To this end, safety data, are regularly reviewed (i.e. after each cohort of patient enrollment) but also other clinical parameters are reviewed, to learn and adjust study design when necessary and as appropriate.

Based on this perspective it is the goal to obtain an adequate number of observations in each study arm, with emphasis on the learning from DIALIVE treatment. Future trials will be defined to assess the efficacy of DIALIVE treatment to the appropriate extend.

4.3 Risks and anticipated adverse device effects that are to be assessed

The oXiris® and septeX™ dialysers are going to be clinically assessed for their safety and performance in relation to the intended goal of removing oxidized albumin and endotoxins in a combined method. For this, the described system will be applied in a specific patient population, i.e. Acute-On-Chronic Liver Failure patients.

The following elements are addressed in the clinical Investigation to mitigate the risk of use:

- The system is only used by a few, selected, qualified and trained investigators already familiar with the haemodialysers and with the Prismaflex;
- The CIP specifies further ICU/HDU monitoring requirements: liver function, haematology, coagulation factors, platelet count, cardiovascular function, cerebral function, renal function, pulmonary function; albumin function, immune function;

Clinical Investigation Plan	CIP YAQ-002	Version: 7.0 10 October 2019
-----------------------------	-------------	------------------------------

- The IB and IFU provides further set-up and priming instructions for the DIALIVE system and additional information will be provided to the investigators as clinical experience will demonstrate to optimize the patient's treatment;
- The CIP is designed to minimize risk of exacerbating symptoms and in line with standard of care, i.e. there are no specific clinical trial procedures to be applied other than haemodialysis while there are multiple health checks build in to monitor the patient's condition;
- The CIP provides organisation control for the patient, i.e. patient treatment on the HDU or /ICUunit per local standard medical practice but with adequate monitoring capabilities.

5 Design of the clinical investigation

5.1 General

This is a European, multi-centre, randomised, controlled, study to generate data for the evaluation of safety (as measured by the percentage of subjects who experience at least one serious adverse event (SAE)) and performance (as measured by plasma endotoxin concentrations and albumin function) of the DIALIVE in 30 evaluable patients with Acute on Chronic Liver Failure (ACLF) versus standard of care (SOC). The study will therefore be open label. The design is appropriate for the study as the primary outcome is to assess safety of the device on a small group of patients.

5.1.1 Measures taken to minimize or avoid bias

The trial is being conducted by investigators who have no direct association with the inventor or the sponsor to ensure no bias is introduced.

5.1.2 Primary Endpoints

The goal is to evaluate the percentage of subjects who experience at least one (1) serious adverse event (SAE) between study Day 1 and Day 10; especially the incidence rate of SAE between the study groups occurring in the period of Day 1 to Day 10.

The percentage of subjects who discontinued DIALIVE due to a serious adverse device event (SADE) between Day 1 (first day of treatment) and Day 10 (DIALIVE arm only)¹⁰.

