Primary End Point	To evaluate the safety of the DIALIVE in patients with Acute on chronic liver failure (ACLF)	The percentage of subjects who experience at least one (1) serious adverse event (SAE) between study Day 1 and Day 10; especially the incidence rate of SAE in both arms of the study at Day 1 and Day 10. The percentage of subjects who discontinued DIALIVE due to a serious adverse device event (SADE) between Day 1 (first day of treatment) and Day 10 (DIALIVE arm only).
Secondary End Point(s)	To evaluate the impact of biochemical performance outlined hereunder towards clinical benefit for patients receiving DIALIVE treatment plus Standard of Care vs Standard of Care alone	 Mortality: 28-days and 3 months Change in ACLF Grade Change in CLIF-ACLF score Improvement in individual organ function: brain (HE), kidney (serum creatinine), CVS (mean arterial pressure), pulmonary (P/F ratio or S/F if arterial blood gas info is not available), liver (serum bilirubin) and coagulation (INR and platelet levels). Status of ICU and Hospital Discharge (including discharge to a hospice for palliative care). Lengths of stay in ICU and hospital at D28 and D90. ICU and hospital re-admissions with another episode of ACLF up to 90 days post randomization.

Clinical Investigation Plan	CIP YAQ-002	Version: 7.0 10 October 2019
-----------------------------	-------------	------------------------------

Secondary end	Objectives	Outcomes Measures
Point(s)	To evaluate the performance of the DIALIVE in patients with ACLF	 Change in Plasma endotoxin level (endotoxin activity and endotoxin concentration) between; Study D1,D3, D5 and D10 across SOC arm
		2. Study D1, D3, D5 and D10 across DIALIVE arm
		Start and end of a treatment session with
		DIALIVE on D1, D2 and D3 4. Study D1, D3, D5 and D10 between SOC and DIALIVE arms for patients with the same grade of ACLF at the time of inclusion in the study
		Target-Value (TV): 40% reduction; Acceptable-Value (AV): 20% reduction Change in Albumin function (Human non- mercapt albumin -2 (HNA-2) / Human marcapt albumin (HMA) ratio:
		5. Study D1, D3, D5 and D10 across SOC arm6. Study D1, D3, D5 and D10 across DIALIVE
		arm 7. Start and end of a treatment session with DIALIVE on D1, D2 and D3.
		8. Study D1, D5 and D10 between SOC and DIALIVE arms for patients presenting with the same grades of ACLF
		TV: 40% reduction; AV: 20% reduction

Clinical Investigation Plan CIP YAQ-002 Version: 7.0 10 0	October 2019
---	--------------

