For each treatment arm, treatment-emergent AE's, SAEs, SADEs, ADEs, USADEs and DDs will be summarised by organ system and treatment causality. The number and percentage of patients discontinuing the study due to Aes, SAEs, SADEs or other stopping criteria confirmed by the Data Safety Monitoring Board (DSMB) will be summarized for each arm. Secondary and exploratory parameters (changes from baseline at each study visit) will be descriptively analysed by treatment arm by means of the appropriate statistics.

Statistical analyses of safety data will be run when each study cohort is completed and the corresponding results will be communicated to the DSMB. Data extraction at interim time points do not serve study analyses.

Number of Visits

Patients will undergo the following

Screening assessment (up to 72hrs)6

Study Day 0-randomisation (DIALIVE treatment may commence on this day if all day 1

parameters have been met) Study Day 1 assessments7

Study Days 1-10 treatment phase commences and completes

Study Day 5 assessments

Study Day 10 assessments

Study Day 14 assessments

Study Day 28 assessments

Study Day 90 assessments

One treatment will be defined as any duration of exposure to the DIALIVE.

Viral serology results from up to 8 weeks before the screening period will be accepted

⁶ Screening period (post consent) has been set up to 72 hours to allow sufficient time to gather all relevant clinical information for the subject to be eligible to progress to randomisation. However, if this information becomes available sooner, then randomisation can proceed after that time (without having to wait for 72 hours). For further clarity, the plan for gathering the most recent and relevant clinical information, yet not delaying the start of the study is as follows:

a. Thorough clinical examination of the patient and assessment of FBC, U&E, LFT, Coagulation must be repeated during this period. If randomised to the DIALIVE arm FBC, U&E, LFT, Coagulation results from the screening period may be used if performed up to 24 hours prior to starting treatment unless patients' clinical status has changed.

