Microbiology results from samples sent in and up to the previous 72 hours (at commencement of screening) need not be repeated. On the day of screening, if the patient is not septic clinically as determined by the PI, then consent can proceed without having to wait for microbiology results. Likewise, if a patient is deemed to be septic based on clinical grounds without positive microbiological cultures, the PI will determine if it is safe to continue with consent and randomization, and this will be reviewed daily.

Clinical Investigation Plan CIP YAQ-002 Version: 7.0 10 October 2019
--

Per Patient	3 months per patient /39 months for completion of the study. Proposed start Feb 2017.
Duration/Total	Proposed finish Dec 2019
Trial Duration	
Applicable	National and/or local legislation is application, including the new GDPR regulation, and
legislation	especially in view of the inclusion of patients who might become or are unconscious and on the involvement of a legal representatives – if appropriate/allowed.
Legal	The Legal Representative, appointed by the sponsor YAQRIT Ltd, is:
Represenative	FAKKEL-bvba
·	[name]
	[name]
	[name]
	Belgium

d. Liver imaging such as liver ultrasound, doppler studies or CT/MRI scan up to 8 weeks prior will be acceptable unless there has been a significant change in the clinical status dictating repeat imaging.

^{*}Some or all of the above tests may need to be repeated during the screening period should there be any significant change in the clinical status of the patient as assessed by the clinical team.

⁷ May concur with study Day 0 if all assessment parameters (as per the schedule of assessments) have been met. DIALIVE treatment must commence before the end of study day 1.

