Patients presenting with, or developing during the study period, severe actue renal failure requiring renal support, will receive continuous renal replacement therapy (CRRT) as per standard local practices. This would apply to subjects in both SOC and DIALIVE arms. For those in the DIALIVE arm, the same vascular catheter which is used for DIALIVE treatment may be used for CRRT following the completion of the DIALIVE treatment session. It is however envisaged

that increased intensity of dialysis component in the DIALIVE system (from 1lit/hr to 1.5lit/hr) and allowance for fluid removal in the new protocol may delay or remove altogether the need for CRRTin these situations. The decision for additional CRRT would depend on clinical situation and will be taken by the site PI.

DIALIVE arm consists of standard of care (defined above), plus DIALIVE treatment.

A DIALIVE treatment session denotes treatment for the day, whereas A DIALIVE treatment cycle refers to the total number of treatment days.

A DIALIVE treatment **session** = A minimum, cumulative duration of 8 to 10 hrs (± 30 min) of the DIALIVE treatment, thus allowing for breaks which may be planned (for example patients needing to go for imaging) or unplanned (device clotting, issues with vascular access or other any other unplanned reasons). A break within a treatment session (consisting of a cumulative time longer than 4hrs), or a cumulative duration of less than 8 hrs of dialysis during one day constitutes a session failure for that day. A session failure will require to restart the dialysis session within 24 hrs after the end of the previous session and will reset the start of the dialysis cycle.

A DIALIVE treatment **cycle**= Consists of 3 consecutive days of 8-10 hrs of DIALIVE treatment sessions on each day within the 10 day window period. A break of more than 24hrs between each treatment session will require a new baseline (i.e. a new treatment cycle commenced). A second failed treatment session within the 10 day window period would result in patient exlusion. The patient must have completed one successful treatment cycle within the 10 day window period to be considered evaluable.

Day of randomization constitutes study Day 0.

The first treatment session (DIALIVE arm only) must commence before the end of study Day 1. As such, dialysis might also start on the day of randomization which might created confusion as 'the first day of dialysis' then concurs with DAY 0 of the study schedule.

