West Haven grade	Х		Х	Х	Х	Х	Х	Х	
Blood sample for biomarkers including Albumin (HNA2) and Endotoxin Plasma Concentration (initial processing locally, samples are transferred to Biobank Royal Free Hospital for analysis) ²¹			Х	X	Х	Х			
Urine sample for biomarkers (initial processing locally, samples are transferred to Biobank Royal Free Hospital for analysis) ²²			Х	Х	Х	Х			
PBMCs (initial processing locally, samples are transferred to Biobank Royal Free Hospital for analysis) ²³			Х	Х	X	Х			
Endotoxin Activity Assay (local processing and analysis)			Х	Х	Х	Х			

²¹ Blood Biomarker tests: cCK18/M30, flCK18/M65, Caspase 3, Caspase 7, IL-18, soluble CD163, cytokines (TNF-α, IL-6, IL-8, IL-10), chemokines (CX3CL1, CXCL3, CCL2, CCL5) 11 Includes blood for Human non-mercapt albumin -2 (HNA-2) and Endotoxin Plasma Concentration (LAL Assay).

²² Urine Biomarker tests: NGAL, TLR4, IL-18

²³ Peripheral blood mononuclear cells (PBMC) Royal Free Hospital, London only.

DIALIVE Patients Study Procedures	Pre-screening	Screening	ening Treatment Period									
		0-72hrs	Day 0	Day 1 ²⁴	Day 2	Day 3	Day 5	Day 10	Day 14 +/- 2 days	Day 28 +/- 5 days	Day 90 +/- 5 days	
Informed consent ²⁵	X											
Inclusion/exclusion criteria		Х	X ²⁶									
Demographics		Х										
Medical history		Х										
Complete physical examination		Х		X	Х	X	X	X	X	X		
Weight (kg) and height (cm)		Х		X	Х	X	X	X	X	X		
Vital signs ²⁷		Х		Х	Х	Х	Х	Х	X	Х		
12-lead ECG		Х		X								
Viral screen (local laboratory) ²⁸		X										
Clinical laboratory (local laboratory) ²⁹		Х		Х	Х	X	X	X	X	X		
Full infection screen (local laboratory)		Х		Х			Х	X				
Pregnancy test (women only)		Х										
Coagulation (local laboratory) ³⁰		Х		X	Х	X	X	X	X	X		
Randomisation			Х									

²⁴ DIALIVE treatment must commence before end of day 1. DIALIVE treatment may commence on day 0 at the discretion of the investigator. If DIALIVE treatment commences on Day 0, then Day 1 tests must be performed before treatment commences on Day 0 and therefore does not need repeating again on Day 1.

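### For patients who start DIALIVE on Day 0, the protocol does not consistently fix where the primary SAE window begins

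*Protocol*

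**What the plan says.** Section 5.1.2 gives two primary endpoints. The first is the percentage of subjects with "at least one (1) serious adverse event (SAE) between study Day 1 and Day 10", in both arms; the synopsis uses the same window. The second is the percentage discontinuing DIALIVE because of a SADE "between Day 1 (first day of treatment) and Day 10 (DIALIVE arm only"). The synopsis repeats this too.

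Section 2.2 fixes the calendar: "Day of randomization constitutes study Day 0". The first session has to begin before study Day 1 ends, so the first treatment day is Day 0 or Day 1. The footnote to the DIALIVE schedule in 5.4 confirms that "DIALIVE treatment may commence on day 0 at the discretion of the investigator".

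The protocol sees the difficulty. Section 2.2 notes that "dialysis might also start on the day of randomization which might created confusion". Synopsis footnote 7 says of the Day 1 assessments: "May concur with study Day 0 if all assessment parameters (as per the schedule of assessments) have been met". Footnotes 24 and 31 move the Day 1 tests ahead of a Day 0 start, and footnote 33 ties the pre-treatment bloods to the treatment-cycle day. Section 7.1.1 has data from a Day 0 dialysis entered under the eCRF label for Day 1, and uses the treatment date to reconstruct the sessions and identify the dialysis cycle eligible for end-point analysis.

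AEs are recorded from consent (12.5), and SAEs are to be reported in full detail (5.1.5).

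**The concern.** Device safety is the primary objective, and only DIALIVE patients can have device exposure on Day 0. If the primary SAE percentage starts on study Day 1 by the calendar, the first exposed hours of a Day 0 starter are left out of the measure meant to describe device safety. If it starts on the first treatment day, the observation windows of the two arms no longer match. Two analysts, one working by calendar date and one by eCRF visit label, could classify the same event differently, and 5.1.2 would not settle which is right.

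The protocol itself treats this as a period that needs attention. Section 2.2 asks for close senior supervision in the first hours of treatment, and 12.5 lists hypotension among the possibly device-related SAEs seen in the initial sessions.

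**Working it through.** No hypothesis is tested and there is no stated figure to reproduce. The check is a comparison of definitions, a count of days, and a scale for one patient.

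**Start on study Day 1.** Both endpoints run from Day 1 to Day 10, which is 10 calendar days. There is no mismatch.

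**Start on Day 0.** The available readings are:

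| Reading | SAE window, Day 0 starter | SAE window, SOC | Is a Day 0 session covered? |
|---|---|---|---|
| Calendar study Day 1 for SAEs, first treatment day for SADEs | Days 1–10 (10 days) | Days 1–10 (10 days) | SADE endpoint only |
| Treatment day (eCRF label) for both, Day 10 counted from randomisation | Days 0–10 (11 days) | Days 1–10 (10 days) | Both |
| Treatment day for both, Day 10 counted from first treatment | Days 0–9 (10 days) | Days 1–10 (10 days) | Both, with both ends of the window one day earlier than in SOC |
| The gloss merely describes study Day 1 | Days 1–10 (10 days) | Days 1–10 (10 days) | Neither |

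Sections 2.2 and 5.3.6 count the 10-day treatment period from randomisation, which favours the second row over the third. The fourth row sits badly with 2.2 and 7.1.1, both of which separate the first day of dialysis from study Day 1. Under the first row, a SADE on Day 0 that ended treatment would count in the second endpoint and not, as an SAE, in the first.

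**Do the remedies settle it?** Footnotes 7, 24, 31 and 33 deal with assessments and samples. Section 7.1.1 deals with data entry, session timing and the eligible cycle. None of them assigns an SAE onset to the primary window.

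**Scale for one patient.** The main analysis set is the patients exposed to treatment (section 6). One patient whose only SAE to Day 10 begins on Day 0 shifts the DIALIVE percentage by 1/n, where n is the number exposed in that arm. Inputs are 30 evaluable patients randomised 1:1 and a 17% dropout rate (5.1.7), and 8 DIALIVE patients enrolled, of whom 6 were evaluable, at the cohort 2 review (Appendix 7 B).

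- Expected number randomised: 30/(1 − 0.17) = 36.1, about 36.
- No dropouts: n = 15; 1/15 = 6.7 points.
- Dropouts split evenly: n = 36/2 = 18; 1/18 = 5.6 points.
- Appendix 7 ratio: n = 15 × 8/6 = 20; 1/20 = 5.0 points.
- All dropouts in DIALIVE: n = 36 − 15 = 21; 1/21 = 4.8 points.

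These are shifts per patient. Without the number of Day 0 starters and their SAE onset dates, no expected effect can be calculated.

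**The case against.** The best defence is that the intent is clear. Footnote 7 lets Day 1 coincide with Day 0, the schedule footnotes move the Day 1 tests, and 7.1.1 was written to prevent this confusion and refers to end-point analysis. A reader could then take Day 1 as the first treatment day throughout, and the two endpoints would align. A reader might therefore infer from 5.1.2 that the two primary endpoints definitely start on different dates, but that is only one of several readings and the text does not force it.

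The intent does lean towards counting a Day 0 session. Section 7.1.1 nevertheless links the treatment date to the eligible cycle and says nothing about SAE onset, and its relabelling applies only where dialysis took place. Following it gives Day 0 starters a window that SOC patients do not have. The unequal length also carries a condition: with Day 10 counted from first treatment, the window is 10 days again, though shifted.

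It can also be said that assigning onset dates to windows belongs in the SAP. That would hold if the protocol were silent. Here it states the primary windows itself and describes Day 1 in two ways within one section.

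Finally, the analysis is descriptive, the DSMB reviews all safety data, and no event in the document is shown to be affected. This stands, and it limits the weight of the point.

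**Conclusion.** The point holds as an inconsistency in a stated rule. For Day 0 starters the beginning of the primary SAE window is not consistently fixed, and no reading both covers the first session in the SAE percentage and gives the two arms the same window. It should be corrected, but it does not threaten the trial.

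The possible shift is 4.8 to 6.7 percentage points in the DIALIVE arm for each patient whose only SAE to Day 10 begins on Day 0, assuming 15 to 21 exposed patients. The comparison of 11 with 10 days assumes that Day 10 is counted from randomisation.

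Two stronger inferences are not supported. A reader might conclude that early device events would go unreported. They would not, because recording starts at consent and SAEs are reported in full; only the primary percentage is at risk. A reader might also suspect that the two early DIALIVE deaths in Appendix 7 B drop out. Taken as 24 to 36 hours after treatment began, they fall on study Day 1 or later on every reading, and within the window.

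**What to change.** In 5.1.2 and, in the same words, in the synopsis:

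- Define the primary SAE window in both arms as the day of randomisation (Day 0) to the end of study Day 10, with Day 10 counted from randomisation. Assign each event by its SAE onset date and not by eCRF visit label. Onset date is enough; no passage shows that onset time is captured.
- State that the SADE-discontinuation window runs from first exposure, including exposure on Day 0, to the end of study Day 10.

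The SAE window is then 11 calendar days in both arms. The two endpoints may still start on different days for a Day 1 starter, which is harmless because discontinuation cannot precede exposure.

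The cost is a wording amendment, which section 8 requires to be approved before use, made after two cohorts have been reviewed. No new data should be needed, provided the AE records carry an onset date, since recording starts at consent and treatment dates are held. The window will also take in a few DIALIVE events between randomisation and first exposure, and SOC events on Day 0. Reporting the Day 1 to Day 10 percentage alongside would show what the change does.
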